### **9.1 Sample Size**

The sample size for this study will be 40 subjects. This sample size is based on historical experience with similar pilot studies with the goal of informing power calculations for future studies. This study is not formally powered for hypothesis testing. A sample size of 40 subjects will be sufficient for developing further understanding of the endpoints described herein. Sample size calculations account for non-evaluable and drop-out patients.

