#### 9.4 Imaging Analysis

Diagnostic performance of pegsitacianine will be assessed at the level of the specimen by calculating the *ex situ* sensitivity, specificity, PPV, and NPV of pegsitacianine in detecting tumor containing tissue. The *ex situ* fluorescence status of collected SOC and pegsitacianine guided specimens will be compared to the histological analyses of the collected specimens (which is used to determine each sample's status as true/false positive/negative). For determining these operating characteristics, consider the following definitions:

- False positive is defined as “fluorescence was observed on the specimen but the specimen was not found to have tumor via histological analysis”.
- False negative is defined as “no fluorescence was observed on the specimen but the specimen was found to have tumor via histological analysis”.
- True positive is defined as “fluorescence was observed on the specimen and the specimen was found to have tumor via histological analysis”.
- True negative is defined as “no fluorescence was observed on the specimen and the specimen was found not to have tumor via histological analysis”.

The number of specimens in each category (each combination of true/false positive/negative), along with the true/false positive/negative rates (and corresponding exact two-sided 95% confidence intervals) will be reported. These rates will be used to determine pegsitacianine's tumor detection sensitivity, specificity, PPV, and NPV using the following equations:

$$\text{Sensitivity} = \frac{\# \text{ of True Positive Specimens}}{\# \text{ of True Positive Specimens} + \# \text{ of False Negative Specimens}}$$

$$\text{Specificity} = \frac{\# \text{ of True Negative Specimens}}{\# \text{ of True Negative Specimens} + \# \text{ of False Positive Specimens}}$$

$$\text{PPV} = \frac{\# \text{ of True Positive Specimens}}{\# \text{ of True Positive Specimens} + \# \text{ of False Positive Specimens}}$$

$$\text{NPV} = \frac{\# \text{ of True Negative Specimens}}{\# \text{ of True Negative Specimens} + \# \text{ of False Negative Specimens}}$$

These rates will be reported along with exact two-sided 95% confidence intervals.

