## 9.6 Diagnostic Imaging Sensitivity Analyses

In this pilot study we are assuming that any fluorescence is indicative of tumor presence. To assess how the amount of observed fluorescence (e.g., the SBR or TBR) may affect the diagnostic accuracy of pegsitacianine, a receiver operating characteristic (ROC) analysis will be performed on all specimens using the observed thresholds of SBR and TBR. The corresponding ROC curve will be provided along with the area under the curve (AUC).

There is potential for within-subject correlation to bias our estimates of pegsitacianine’s diagnostic accuracy. To assess this issue, an ROC curve will be constructed from a mixed model that clusters specimens by the subject they originated from. We will compare the AUC of the mixed effects ROC curve to the standard ROC curve to assess if within-subject correlation is causing significant bias in our analyses. If it is determined that significant bias has been introduced, additional analyses on secondary endpoints may be performed to assess the diagnostic accuracy of pegsitacianine.

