5.1.2 Diagnostic Imaging Endpoints

Diagnostic performance of pegsitacianine will be assessed by calculating sensitivity, specificity, NPV, and PPV of pegsitacianine in detecting tumor containing tissue. The *ex situ* fluorescence status (any fluorescence vs. no fluorescence) of collected SOC and pegsitacianine guided specimens, as well as lymph nodes, will be compared to histological analyses of the collected specimens. Sensitivity and specificity for detecting tumor-containing tissue versus normal tissue

will be evaluated using tissue specimen fluorescence and the corresponding pathological outcomes.

True/false/negative/positive definitions are as follows:

- False positive is defined as fluorescence was observed on the sample but the sample was not found to have tumor via pathology.
- False negative is defined as no fluorescence was observed on the sample but the sample was found to have tumor via pathology.
- True positive is defined as fluorescence was observed on the sample and the sample was found to have tumor via pathology
- True negative is defined as no fluorescence was observed on the sample and the sample was found not to have tumor via pathology.

Pegsitaricaine sensitivity and PPV will be calculated using the following equations:

$$\text{Sensitivity} = \frac{\text{\# of True Positive Specimens}}{\text{\# of True Positive Specimens} + \text{\# of False Negative Specimens}}$$

$$PPV = \frac{\# \text{ of True Positive Specimens}}{\# \text{ of True Positive Specimens} + \# \text{ of False Positive Specimens}}$$

Pegsiraniline specificity values and NPV will be calculated using the following equations:

$$\text{Specificity} = \frac{\text{\# of True Negative Specimens}}{\text{\# of True Negative Specimens} + \text{\# of False Positive Specimens}}$$

$$NPV = \frac{\# \text{ of True Negative Specimens}}{\# \text{ of True Negative Specimens} + \# \text{ of False Negative Specimens}}$$

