7.9.5 Surgery Details and Specimen Collection

Surgery details including the following will be summarized on a patient level using descriptive statistics in the Safety population:

- Duration of surgery
- Location of tumor

- Method of tumor localization, including number of subjects with primary tumor(s) identified using NIR imaging
- Number of SOC specimens collected
- Number of additional lung nodules/areas found as a result of NIR imaging following SOC procedures and confirmed to be cancer
- Number of SOC specimens collected, found to be negative for tumor, and did not fluoresce during *ex situ* imaging
- Number of areas with fluorescence removed on:
 - Lung resection margins
 - Thoracic cavity
 - Lymph nodes
 - Total (any area)
- Number of areas with fluorescence on lung resection margins
- Subjects with fluorescence observed anywhere in thoracic cavity
- Number of lymph nodes collected as SOC surgery
- Time spent imaging
- Camera system used

A listing will also be generated.

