7.10.2 Secondary Analyses

7.10.2.1 Analysis of Diagnostic Imaging

The positive predictive value, negative predictive value, sensitivity, and specificity (specimen level) will be calculated and summarized for each Part and overall. The summary will include the true/false negative/positive rate and number of specimens. Two-sided 95% confidence intervals will be calculated for each rate via Clopper-Pearson method.

A listing by subject and specimen showing the specimen type (primary tumor/ additional SOC specimen, lung resection margin, thoracic cavity, lymph node), attainment by SOC or fluorescence (if primary/ additional SOC/ lymph), pathology result, fluorescence *in situ* and *ex situ*, and fluorescence measures (MFI and TBR) will be provided.

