7.10.3 Exploratory Analyses

7.10.3.1 Analysis of Fluorescence Intensity

A summary of MFI for the tumor (or suspected tumor), MFI for the normal background tissue, and TBR will be provided by Part and overall for each pathology result (tumor vs. no tumor). This summary will be at the specimen level, meaning each subject may have multiple specimens.

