7.10.3.2 ROC Analysis

In this pilot study we are assuming that any fluorescence is indicative of tumor presence. To assess how the amount of observed fluorescence (e.g., the SBR or TBR) may affect the diagnostic accuracy of pegasitacianine, a receiver operating characteristic (ROC) analysis will be performed on all specimens using the observed thresholds of SBR and TBR. The corresponding ROC curve

will be provided along with the area under the curve (AUC) and the 95% confidence interval of the AUC.

There is potential for within-subject correlation to bias our estimates of pegsitacianine's diagnostic accuracy. To assess this issue, an ROC curve will be constructed from a mixed model that clusters specimens by the subject they originated from. We will compare the AUC of the mixed effects ROC curve to the standard ROC curve to assess if within-subject correlation is causing significant bias in our analyses. If it is determined that significant bias has been introduced, additional analyses on secondary endpoints may be performed to assess the diagnostic accuracy of pegsitacianine.

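### The exact intervals for specimen-level sensitivity, specificity, PPV and NPV treat specimens from the same patient as independent, and the planned AUC comparison does not detect the resulting loss of coverage

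*SAP*

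**What the plan says.** SAP 7.10.2.1 calculates the four performance rates at specimen level: "Two-sided 95% confidence intervals will be calculated for each rate via Clopper-Pearson method". Protocol 9.4 plans the same: "These rates will be reported along with exact two-sided 95% confidence intervals". Neither section has a term for patient.

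Several specimens per patient are expected. SAP 5.1.2 pools standard-of-care (SOC) and fluorescence-led material: the SOC and "guided specimens, as well as lymph nodes, will be compared to histological analyses of the collected specimens". SAP 7.9.5 summarises per-patient counts, including "Number of lymph nodes collected as SOC surgery". SAP 7.10.3.1 notes that "each subject may have multiple specimens".

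Protocol 9.6 and SAP 7.10.3.2 acknowledge within-subject correlation, but as a possible source of bias in diagnostic accuracy. The check is to compare the AUC of a mixed-model ROC curve, clustered by subject, with the AUC of the ordinary one. Protocol 9.6 then says: "If it is determined that significant bias has been introduced, additional analyses on secondary endpoints may be performed". The SAP repeats this. Neither document gives a criterion for significant bias or names the further analyses.

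**The concern.** Two specimens from one patient share the dose received, the time since infusion, the camera, the surgeon who makes the fluorescence call, and the patient's own background signal. If these make the calls positively correlated, n specimens carry less information than n independent trials. Clopper-Pearson on the raw count then gives an interval that is too short.

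The planned AUC comparison concerns a different quantity. It looks for a shift in the accuracy of a continuous measure (SBR or TBR), whereas the problem is the interval width for a yes/no call. Its consequence is also optional.

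At stake is the apparent precision of the only named secondary efficacy metrics. Protocol 9.1 justifies the sample size "with the goal of informing power calculations for future studies". A later specimen-level study would need the ICC or design effect for that purpose, and the plan reports neither.

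**Working it through.** **Figures in the plan.** The 40 subjects rest on historical experience, with no rate, power or precision target, so there is no calculation to reproduce. The figure that can be checked is the nominal 95% level.

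**Inputs.** From the documents: 40 subjects (SAP 4), two-sided 95% level (SAP 7.2), Clopper-Pearson (SAP 7.10.2.1). Assumed, because the documents give no values: true rate 75%; m specimens per patient in the denominator, equal across patients; beta-binomial outcomes with ICC 0.1, 0.3 or 0.5.

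**Step 1: independent specimens.** At ICC 0, coverage of the planned interval is 95.5% to 97.2% for m from 1 to 8. The method is sound when its assumption holds.

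**Step 2: correlated specimens.** The distribution of total successes is the convolution of 40 beta-binomials. Coverage is the probability that the planned interval contains 75%.

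| m | ICC 0.1 | ICC 0.3 | ICC 0.5 |
|---|---|---|---|
| 1 | 97.2% | 97.2% | 97.2% |
| 2 | 95.1% | 93.0% | 90.8% |
| 3 | 94.6% | 90.4% | 86.3% |
| 5 | 91.6% | 83.1% | 76.1% |
| 8 | 87.6% | 74.4% | 65.3% |

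A separate simulation with 20 or 40 contributing patients and true rates of 70% to 90% shows the same pattern. At ICC 0.2, coverage is 93.8% to 96.1% for m=2, 89.8% to 92.8% for m=4, and 80.6% to 82.7% for m=8.

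**Step 3: width.** With equal m the design effect is DEFF = 1 + (m−1) × ICC, and the half-width should grow by about √DEFF. For m=5 and ICC 0.3, DEFF = 1 + 4 × 0.3 = 2.2 and √2.2 = 1.48. Mean half-widths in percentage points, planned against clustered:

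- m=2, ICC 0.1: 9.9 against 10.5 (ratio 1.06)
- m=3, ICC 0.3: 8.0 against 10.2 (1.27)
- m=5, ICC 0.3: 6.2 against 9.3 (1.50)
- m=8, ICC 0.5: 4.8 against 10.5 (2.17 before rounding)

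As an illustration, take 160 specimens, 4 from each of 40 patients, and an observed rate of 80%. The planned interval is 73.0% to 85.9%. At ICC 0.3, DEFF = 1 + 3 × 0.3 = 1.9, the effective n is 160/1.9 = 84.2, and the interval is 69.9% to 87.9%.

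**Step 4: does the AUC comparison see this?** A random-intercept logistic model of tumour status on fluorescence signal was fitted to simulated data (40 patients, 4 specimens each). The SAP does not say which predictions form the mixed-model ROC curve, so both readings were tried.

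- *Fixed-effect predictions:* the two AUCs were identical in every fit, because a single predictor is only transformed monotonically. Specificity coverage was meanwhile 92.1% at signal ICC 0.3 and 90.0% at 0.5.
- *Predictions including the patient effect:* the AUC rose by 0.016 with no correlation at all. It rose by 0.072 when only tumour status was clustered, where coverage was intact (specificity 95.9%, sensitivity 96.9%). It rose by 0.058 at signal ICC 0.3, where specificity coverage was 92.1%.

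The AUC difference can therefore be zero while coverage fails, and largest while coverage holds.

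**The case against.** The strongest reply is that the size is assumed. A sensitivity denominator may hold little more than one primary tumour per patient, and at m=1 nothing is lost. At m=2 with ICC 0.1, coverage is still 95.1%. The large losses are more plausible for specificity, where negative lymph nodes accumulate. PPV and NPV have random denominators and were not simulated separately. All of this stands: no single coverage figure can be attributed to this trial.

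Second, these are secondary, descriptive rates in a pilot with no hypothesis test. The primary rate is per subject, the 70% condition for opening Part 2 sets no interval requirement, and Part 2 was not opened. This also stands and limits the severity. It does not justify an independence interval for data that the plan itself regards as possibly correlated.

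Third, the planned listing by subject and specimen would let a later planner derive the ICC. That softens the argument about future studies but does not correct the reported intervals.

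Fourth, a corrected interval has limits of its own. At m=8, the effective-sample-size interval covers 89.4% and 83.7% (ICC 0.3 and 0.5) with 20 contributing patients and a true rate of 95%. With 40 patients and a rate of 98%, it covers 87.6% and 78.5%. High rates are not far-fetched, since Protocol 1.2 cites 100% sensitivity in the earlier Phase 1 study. Even so, the planned interval covers only about 67% to 79% in those cells. The limitation should be disclosed, and another prespecified patient-clustered method would also answer the concern.

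**Conclusion.** The concern holds. As written, the four specimen-level rates get intervals that assume independence, and they under-cover when a denominator holds more than one specimen per patient and those specimens are positively correlated. The planned AUC comparison neither measures nor corrects this.

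Under the stated assumptions (40 patients, equal m, beta-binomial, rate 75%), the loss is nil at m=1 and at m=2 with ICC 0.1. It is about 5 percentage points at m=3 with ICC 0.3 (95 − 90.4 = 4.6) and about 12 at m=5 with ICC 0.3 (95 − 83.1 = 11.9). Confidence is high in the mechanism; the size in this trial depends on m and the ICC, which the documents do not give. The plan should be corrected, but the fault does not threaten the primary result.

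**What to change.** In SAP 7.10.2.1 and Protocol 9.4, make a patient-clustered interval the main one for each specimen-level rate:

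1. For a denominator of n specimens from K patients, with x_i successes among n_i specimens in patient i and p = Σx_i/n, compute the linearized variance V = [K/(K−1)] × Σ(x_i − p·n_i)²/n². Then DEFF = V / [p(1−p)/(n−1)] and n* = n / max(1, DEFF).
2. Compute Clopper-Pearson with p × n* events out of n*.
3. If all specimens in a denominator agree, DEFF cannot be estimated. Set it to 1 and flag the interval as unadjusted.
4. Apply this whatever the AUC comparison shows.
5. For each denominator, report the number of patients, specimens per patient, and DEFF or ICC.

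Keep plain Clopper-Pearson for the subject-level rate in SAP 7.10.1.1. If the protocol is not amended, record the change in SAP 8, which now says that no deviations are planned.

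In 20,000 simulated runs per cell (40 patients, equal m from 1 to 8, ICC 0.1 to 0.5), this interval covers 95.2% to 97.2% at a true rate of 75% and 94.7% to 97.5% at 90%. At 95% with ICC 0.5 and m from 2 to 8, it covers 91.5% to 94.1%, against 66% to 91% for the planned interval. At m=1, DEFF is exactly 1 and the two intervals coincide.

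The cost is a paragraph in each document and a short SAS step. No new data are needed, because the listing by subject and specimen is already planned. Intervals will be wider, and the text should state that coverage can still fall short at rates near 95% or above with high ICC, more so with few contributing patients.

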7.10.3 Exploratory Analyses

7.10.3.1 Analysis of Fluorescence Intensity

A summary of MFI for the tumor (or suspected tumor), MFI for the normal background tissue, and TBR will be provided by Part and overall for each pathology result (tumor vs. no tumor). This summary will be at the specimen level, meaning each subject may have multiple specimens.

7.10.3.2 ROC Analysis

In this pilot study we are assuming that any fluorescence is indicative of tumor presence. To assess how the amount of observed fluorescence (e.g., the SBR or TBR) may affect the diagnostic accuracy of pegasitacianine, a receiver operating characteristic (ROC) analysis will be performed on all specimens using the observed thresholds of SBR and TBR. The corresponding ROC curve

will be provided along with the area under the curve (AUC) and the 95% confidence interval of the AUC.

There is potential for within-subject correlation to bias our estimates of pegsitacianine's diagnostic accuracy. To assess this issue, an ROC curve will be constructed from a mixed model that clusters specimens by the subject they originated from. We will compare the AUC of the mixed effects ROC curve to the standard ROC curve to assess if within-subject correlation is causing significant bias in our analyses. If it is determined that significant bias has been introduced, additional analyses on secondary endpoints may be performed to assess the diagnostic accuracy of pegsitacianine.

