Sample Size	
N=40
 
Up to 40 patients will be enrolled in this study. No set allocation of patients to Part 1 and Part 2 will be implemented, rather Part 2 will be opened at the discretion of the sponsor following the demonstration of satisfactory pegsitacianine sensitivity and specificity values of 70% or greater in Part 1. The sponsor reserves the right to perform an interim analysis following early enrollment (i.e., <math>n \leq 10</math> patients) to determine the feasibility and benefit of pegsitacianine as an adjunct to standard of care lung malignancy resection.

Statistical Analysis	
The quotient of patients with a CSE over the total number of patients undergoing surgery who received any dose of the study drug, and had sufficient imaging data (minimum of 1 collected image). Sensitivity and specificity will be determined at the specimen level based on correlated fluorescence status and pathological outcome.
 
Pegsitacianine performance data will be evaluated in toto, as well as separately if Part 2 of the study is opened to enrollment. Part 1 and Part 2 data will be evaluated independently to assess performance when using different imaging systems within their respective procedure (i.e., minimally invasive vs. open).

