## **14. APPENDIX 2: FDA-CLEARED NIR IMAGING DEVICES**

**NOTE:** this list is not comprehensive and does not restrict the use of other FDA-cleared imaging device from use in this trial.

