3. STUDY DESCRIPTION

3.1 Study Design

This Phase 2 study will be an interventional, open-label, single arm trial where each patient is his/her own “intrapatient” control. All patients will receive a single █ mg/kg dose of pegsitacianine administered █ prior to standard of care (SOC) surgery. The study will be conducted in two Parts. Part 1 will enroll patients undergoing minimally invasive procedures (i.e., video-assisted thorascopic surgery [VATS] or robotic surgery). Part 2 will be opened at the discretion of the Sponsor and include patients undergoing open thoracotomy for the removal of their disease. [Note: Part 2 was not opened to enrollment.]

Patients will have a biopsy confirmed diagnosis, or a high clinical suspicion of a lung malignancy based on CT and/or PET imaging. A total of up to 40 patients will be enrolled in this trial. The sponsor reserves the right to perform an interim analysis following early enrollment (n ≤ 10 subjects) to determine the feasibility and benefit of pegsitacianine as an adjunct to SOC surgery.

The surgeon will attempt to perform their SOC resection of visible tumors. If the tumor is unable to be located under standard white light conditions, an appropriate near-infrared (NIR) imaging device may be used to aid in the location of the primary tumor. Localization of the primary tumor using NIR imaging in conjunction with pathology confirmed presence of disease will be considered a clinically significant event.

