7.2 Reporting Conventions

The following conventions will be applied to all data presentations and analyses:

- Continuous variables will generally be summarized by the number of patients with missing and non-missing values, mean, standard deviation, median, Q1 (quartile 1), Q3 (quartile 3), minimum, and maximum.
- Categorical variables will be summarized by the number and percentage of patients within each category. If not specified otherwise, the number of patients with non-missing values will be the denominator for percentage calculations. The number of patients with missing values will be presented.
- Confidence intervals will be reported as two sided at the 95% level.
- All mean and median values will be formatted to one more decimal place than the measured value.
- Standard deviation values will be formatted to two more decimal places than the measured value.
- Minimum and maximum values will be presented with the same number of decimal places as the measured value.
- The number and percent of responses will be presented in the form XX (XX %), where the percentage is in parentheses. Percentages will be rounded to the nearest percent. In

the case of a frequency of zero, the frequency and percentage will be presented as 0 rather than 0 (0%).

- Date variables will be formatted as DDMMYY for presentation

All the analyses will be run displaying the results from Part 1. All rates will be summarized using counts and percentages.

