7.10.3.3 Camera System Analysis

An analysis on diagnostic results by camera system will be performed. 2x2 incidence tables comparing the true/false negative/positive results will be constructed for each camera system, and compared via the Breslow-Day test to assess if there is any effect of camera system on diagnostic results (e.g. to test if the common odds-ratio of each incidence table is equivalent across camera types). A summary including the diagnostic true/false negative/positive numbers and rates for each camera system, sensitivity, specificity, and p-value of this analysis will be provided.

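### The fluorescence summaries and the ROC curve pool all NIR cameras; the camera analysis should be extended from the yes/no result to MFI and SBR

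*SAP*

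**What the plan says.** **Cameras allowed.** SAP 3.1 states that "Part 1 will enroll patients undergoing minimally invasive procedures (i.e., video-assisted thorascopic surgery [VATS] or robotic surgery"), so one Part holds two kinds of minimally invasive surgery. Protocol Appendix 2 gives five example devices, among them a laparoscopic system (PINPOINT) and, separately, da Vinci Firefly. It adds that "this list is not comprehensive and does not restrict the use of other FDA-cleared imaging device". The Protocol Summary allows up to 5 centers.

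**Separation by Part.** The Protocol Summary (Statistical Analysis) says "Part 1 and Part 2 data will be evaluated independently to assess performance when using different imaging systems". SAP 3.1 then records that "Part 2 was not opened to enrollment", and SAP 7.2 that "All the analyses will be run displaying the results from Part 1".

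**Intensity analyses.** Under SAP 7.10.3.1, a summary of tumor MFI, "MFI for the normal background tissue, and TBR will be provided by Part and overall for each pathology result". Under SAP 7.10.3.2, the ROC "analysis will be performed on all specimens using the observed thresholds of SBR and TBR". A second ROC comes from a mixed model that clusters specimens by subject, and its AUC is compared with the standard one. Neither section names camera. SAP 7.6 also rules out any analysis by center.

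**Camera analysis.** SAP Table 1 lists the effect of camera system on diagnostic results as an exploratory objective. Under SAP 7.10.3.3, "2x2 incidence tables comparing the true/false negative/positive results will be constructed for each camera system", with sensitivity and specificity per camera and a Breslow-Day test. SAP 7.9.5 lists the camera system used among the patient-level surgery details.

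**The concern.** MFI is read in the units of the camera that took the image. SBR (SAP 5.1.3) divides by the MFI of normal tissue, which removes a pure difference in gain but not an additive offset.

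The protocol treated the imaging system as a reason to analyze groups of patients apart, and relied on the Part split to do so. With Part 2 unopened, the by-Part and overall columns are the same pool, and that pool may contain several cameras. The SAP accepts that camera may matter for the yes/no call, yet leaves it out of the measurements that depend on the camera most directly.

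At stake is the exploratory objective of relating SBR to diagnostic accuracy. A pooled ROC compares every tumor specimen with every non-tumor specimen, including pairs imaged on different cameras. If the cameras read differently, those pairs reflect the camera as well as the tissue. Protocol 9.1 says the study is meant to inform power calculations for later studies, and an AUC that depends on this trial's camera mix may not carry over to them.

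**Working it through.** The documents give no target AUC, no number of specimens per camera and no SBR distribution by camera. There is therefore no planned figure to reproduce, and what follows shows direction and size on assumed inputs.

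**1. Raw MFI and SBR under gain and offset.** Take a true signal of T = 300 in the specimen and N = 100 in normal tissue (assumed), with MFI = g×T + b and SBR = (g×T + b)/(g×N + b).
- Gain g = 0.5, 1, 2 with b = 0: specimen MFI = 150, 300, 600; SBR = 3.0 each time.
- Gain 1 with b = 20, 50, 100: SBR = 320/120 = 2.67, 350/150 = 2.33, 400/200 = 2.00.

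Gain alone makes pooled MFI uninterpretable but leaves SBR intact. An offset moves SBR.

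**2. Pooled AUC.** Assumed: two cameras, A and B, with 100 specimens each. Log-SBR is normal with SD 1, the AUC on each camera is 0.85, and camera B reads s SD higher.
- Separation between tumor and non-tumor: d = √2 × Φ⁻¹(0.85) = 1.466.
- Let wt and wn be camera B's share of the tumor and of the non-tumor specimens.
- Pooled AUC = [wt·wn + (1−wt)(1−wn)] × 0.85 + wt(1−wn) × Φ((d+s)/√2) + (1−wt)wn × Φ((d−s)/√2).
- For s = 1, Φ((d+s)/√2) = 0.959 and Φ((d−s)/√2) = 0.629.

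| Shift s | Tumor prevalence, A / B | wt | wn | Pooled AUC |
|---|---|---|---|---|
| 0 | any | any | any | 0.850 |
| 0.5 | 25% / 25% | 0.50 | 0.50 | 0.843 |
| 1 | 25% / 25% | 0.50 | 0.50 | 0.822 |
| 2 | 25% / 25% | 0.50 | 0.50 | 0.761 |
| 1 | 15% / 40% | 40/55 = 0.727 | 60/145 = 0.414 | 0.872 |
| 1 | 40% / 15% | 15/55 = 0.273 | 85/145 = 0.586 | 0.768 |

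For example, row 3 is 0.50 × 0.85 + 0.25 × 0.959 + 0.25 × 0.629 = 0.822. Row 5 is 0.461 × 0.85 + 0.426 × 0.959 + 0.113 × 0.629 = 0.872. In row 6 the last two weights change places, which gives 0.768.

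An AUC built only from within-camera pairs is 0.85 in every row, because the cross-camera terms drop out.

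**3. Whether SAP 7.10.3.3 would catch this.** It reports no MFI, SBR or AUC by camera. Its test compares odds ratios, which a shift in the effective threshold can leave unchanged. Suppose each camera has 30 tumor and 30 non-tumor specimens (assumed):
- Sensitivity/specificity 0.90/0.50: OR = (27×15)/(3×15) = 9.
- Sensitivity/specificity 0.50/0.90: OR = (15×27)/(15×3) = 9.

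Breslow-Day p = 1.0. The per-camera sensitivity and specificity would show the difference, but only for the yes/no call.

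**The case against.** The other side has good points, and most of them limit the concern.

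- **Only exploratory output is touched.** The primary CSE rate uses no SBR. Sensitivity, specificity, PPV and NPV rest on any fluorescence versus none (SAP 5.1.2). The interim review in Protocol 9.8 does look at MFI and TBR, but ties its decision to no single endpoint. This stands, so a reader should not infer that the main results are at risk.
- **No cut-off is planned.** It is tempting to say that an SBR threshold from the pooled curve would fail on individual cameras. SAP 7.10.3.2 plans a curve and an AUC over observed thresholds; it selects no cut-off and carries none forward. That stronger reading is not supported.
- **Bias is not shown.** The documents do not say which cameras were used, in what mix, or whether SBR differs between them. Allowing several devices is not evidence that several were used. This stands, and the conclusion has to be conditional.
- **The effect may lie within sampling error.** With 50 tumor and 150 non-tumor specimens at AUC 0.85, the Hanley-McNeil standard error is about 0.036, or ±0.07 at 95%. At equal prevalence, the move to 0.843 or 0.822 is smaller than that. This stands for modest shifts with a balanced mix; the unbalanced rows move by 0.02 and 0.08.
- **Camera is not ignored, and the mixed model may help.** Camera is a stated objective with its own section. If each patient is imaged on one camera, clustering by subject may absorb or reveal part of a camera shift. It would not attribute that shift to camera, and the standard ROC stays pooled. Planned listings would allow a split by hand, but no such summary is specified.

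What survives is a narrow gap: the plan examines camera for the yes/no call and not for the intensity measures.

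**Conclusion.** The gap holds on the text. MFI, SBR/TBR and the ROC are pooled over cameras, and the Part split no longer separates imaging systems.

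The consequence is conditional. If more than one camera was used, an overall raw MFI has no common unit; that is the firmest part. If SBR distributions also differ by camera, the pooled AUC can be too low or too high. With an assumed within-camera AUC of 0.85 and a 1 SD shift, it is 0.82 at equal prevalence and 0.77 or 0.87 at 15% versus 40%, depending on which camera has more tumors. With no shift it is unbiased. The shift, the mix and the within-camera AUC are all assumptions.

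This is an inexpensive improvement to exploratory analyses. It is not a defect in the primary or secondary results.

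**What to change.** - **SAP 7.10.3.1:** tabulate MFI, background MFI and SBR by camera system and pathology result.
- **SAP 7.10.3.2:** beside the pooled ROC, report one camera-stratified AUC that compares tumor with non-tumor specimens only within the same camera: Σ(mₖ·nₖ·AUCₖ)/Σ(mₖ·nₖ), where mₖ and nₖ are the tumor and non-tumor specimens on camera k. Give per-camera AUCs descriptively where numbers allow.
- **Do not** add camera as a fixed effect to a model that predicts tumor status. Differences in tumor prevalence between cameras would then feed into the predicted values and so into the AUC.

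No new data are needed if each patient is imaged on one camera, since the camera is already recorded. If a patient can be imaged on more than one, the camera must be linked to each specimen.

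The cost is SAP wording and a few table rows. Per-camera AUCs will be imprecise with at most 40 patients: with 25 tumor and 75 non-tumor specimens at AUC 0.85, the standard error is about 0.05 (±0.10) before any allowance for clustering. The stratified AUC loses less, because it combines all within-camera pairs.
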